8.3 Randomization

Nationwide Children's Hospital pharmacy will serve as the lead pharmacy. Randomization will be determined via the lead pharmacy. Subjects at each site will be randomized 1:1 to receive treatment with either prednisolone at 0.75 mg/kg/day (or weekend dosing per sites standard of care) or spironolactone at 1mg/kg/day. Subjects will be assigned treatment sequentially from the provided list. Subjects will not be randomized until the echocardiogram and all lab results are finalized and reviewed by the Study Doctor.

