8.4 Baseline Assessment of Endpoints

After obtaining informed consent and completing the registration procedures, baseline subject history data will be collected, including records of all medications and supplements that the subject is taking. The following assessments will be performed to confirm subject eligibility for this trial. Screening tests must be completed prior to treatment administration as described in the study timeline. Screening testing includes the following, which are discussed in detail below:

- 100 meter timed test (100M)
- Strength testing and dynamometry
- North Star Ambulatory Assessment (NSAA)
- 4-stair climb
- Time to arise from floor
- Echocardiogram
- Baseline laboratory testing

The subject and his parents will be aware that his participation may be terminated after any of these screening procedures.

There is no central laboratory for this trial. Site-specific normal lab ranges will be documented in respective sites' regulatory binders. Lab ranges will be provided by each site's laboratory. Laboratory tests with values within the clinically significant range will be repeated during the same visit whenever possible. If the test result returns after the subject leaves the clinic, they will be immediately contacted. Subjects will be asked to return to the outpatient clinic for a repeat test. For non-local subjects, arrangements can be made to have the blood test redrawn in a laboratory close to home or by their primary care physician. If still out of the range and clinically significant, the subject may be terminated from the study following discussion with the Clinical Safety Monitor.

To avoid any confusion for the primary care physician, he or she will be informed (with permission from the subject) of their participation in the trial at the time of enrollment.

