8.5 Subject Withdrawal Criteria

Subjects meeting the following criteria will be withdrawn from the trial:

1. Unable to tolerate study medication.
2. Failure to keep an accurate medication log.
3. Failure to keep study appointments.
4. Missing more than 10% of prescribed doses of study medication.*

**If a subject is missing more than 10% of prescribed doses, a discussion about the subject's continuation in the trial will take place between the Principal Investigator and the Sponsor-Investigator.*

Corticosteroids are the standard of care for the treatment of Duchenne muscular dystrophy and have a well-known side effect profile (see section 9.3). Subjects with any Grade 1 or higher (according to the Common Terminology Criteria for Adverse Events (CTCAE) version 4.03 and listed in section 11.1) adverse events that are anticipated and related to prednisolone use, will continue in the trial. Subjects with any Grade 2 or higher adverse events that are anticipated and are possibly, probably or definitely related to spironolactone use will have the study drug held and will be re-challenged in 1 week. If a subject experiences a recurrence of the adverse event, he may be withdrawn after discussion with the Clinical Safety Monitor. Subjects with any Grade 2 or higher adverse events that are unanticipated, may be withdrawn after discussion with the Clinical Safety Monitor. The Principal Investigator will determine a clinically appropriate tapering regimen with respect to assigned study drug and length of time on drug.

Principal Investigators must report all participant withdrawals to the Sponsor-Investigator within 48 hours of learning of the withdrawal. The Sponsor-Investigator will then notify the Clinical Safety Monitor of the withdrawal within 3 business days of the Sponsor-Investigator learning of the withdrawal.

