10.1 Laboratory Procedures/Evaluations

Laboratory tests with values within the clinical significant range may be repeated during visits whenever possible. If the test result returns after the subject leaves the clinic and the Study Doctor wants additional tests, they will be immediately contacted. Subjects may be asked to return to the outpatient clinic for a repeat test. For non-local subjects, arrangements can be made to have the blood test redrawn in a laboratory close to home or by their primary care physician.

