11.1.3 Serious Adverse Event (SAE)

An adverse event or suspected adverse reaction is considered “serious” if, in the view of either the Sponsor-Investigator or Principal Investigator, it results in any of the following outcomes: death, a life-threatening adverse event, inpatient hospitalization or prolongation of existing hospitalization, a persistent or significant incapacity or substantial disruption of the ability to conduct normal life functions, or a congenital anomaly/birth defect. Important medical events that may not result in death, be life-threatening, or require hospitalization may be considered serious when, based upon appropriate medical judgment, they may jeopardize the subject and may require medical or surgical intervention to prevent one of the outcomes listed in this definition. Examples of such medical events include allergic bronchospasm requiring intensive treatment in an emergency room or at home, blood dyscrasias or convulsions that do not result in inpatient hospitalization, or the development of drug dependency or drug abuse. **A serious adverse events refers to a grade of 3, 4, or 5.**

All SAEs that occur after any subject has signed informed consent, before treatment, during treatment or within 30 days following the last study visit, whether or not they are related to the trial must be recorded.

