If a serious adverse event occurs within 30 days after a subject's final study visit and is determined to be unexpected and related to the use of either study drug, that event will be reported to the Reviewing IRB within **3 business days** of the Sponsor-Investigator learning of the determination.

Should a serious adverse event deemed possibly, probably or definitely related to the study agent occur during administration, the study agent will be discontinued, appropriate treatment will be given under medical supervision and the subject will be examined as frequently as necessary thereafter until symptoms cease or stabilize.

All new information and significant noncompliance indicating a new or increased risk or new safety issue as defined in the Reviewing IRB policies will be reported to the Sponsor-

Investigator within **48 hours** of the Principal Investigator learning of the information. The Sponsor-Investigator will report to the Reviewing IRB within **3 business days** of the Sponsor-Investigator's initial receipt of the information. This includes deviations from the protocol that harmed subjects or others or that indicates subjects or others might be at an increased risk of harm.

The Sponsor-Investigator will inform the Clinical Safety Monitor of all serious adverse events regardless of severity, relatedness, or expectedness and of all instances of significant non-compliance impacting patient safety within **48 hours** of the Sponsor-Investigator's initial receipt of the information.

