11.4 Study Discontinuation Rules

An independent Clinical Safety Monitor will monitor safety data on a continual basis throughout the trial. The Clinical Safety Monitor can recommend early termination of the trial for reasons of safety. Study enrollment will be halted by the Principal Investigators when any subject experiences a Grade 3 or higher adverse event toxicity that is unanticipated and possibly, probably, or definitely related to the study drug that presents with clinical symptoms and requires medical treatment. This will include any subject death, hospitalization, or important clinical laboratory finding. If after review by the Clinical Safety Monitor and the Reviewing IRB, the decision is made to continue, the trial will proceed according to Section 10 of this protocol.

Anticipated adverse events related to progression of Duchenne muscular dystrophy may include muscle weakness, elevated creatine kinase levels, loss of ambulation, scoliosis, short stature, and intellectual disability.

Anticipated adverse events related to prednisolone treatment, which is the standard of care, may include weight gain, cushingoid features, long bone fractures, acne, behavioral disturbance, and short stature (see section 9.3.2 for additional potential side effects).

Anticipated adverse events related to spironolactone treatment may include increased potassium levels, increased breast tissue mass, diarrhea, cramping, nausea, vomiting, headache, sleepiness, unsteadiness, and urticaria (see section 9.3.1 for additional potential side effects).

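### Section 8.5 mandates spironolactone re-challenge at a fixed 1 week without requiring improvement or a repeat potassium, and for related Grade 3 or 4 events it conflicts with Section 11.3.2

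*Combined protocol and SAP*

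**What the plan says.** For any Grade 2 or higher event that is anticipated and at least possibly attributed to spironolactone, Section 8.5 directs that subjects with events related to "spironolactone use will have the study drug held and will be re-challenged in 1 week". The sentence has no upper grade. If the event comes back, the boy may be withdrawn after discussion with the Clinical Safety Monitor; nothing is asked for before the restart.

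Section 11.4 lists as anticipated with spironolactone "increased potassium levels, increased breast tissue mass, diarrhea, cramping, nausea, vomiting, headache, sleepiness, unsteadiness, and urticaria". Raised potassium therefore falls under the re-challenge sentence.

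For higher grades, Section 11.1.3 states: "A serious adverse events refers to a grade of 3, 4, or 5". Section 11.3.2 states that, should a serious event at least possibly related to the study agent "occur during administration, the study agent will be discontinued". Neither section refers to 8.5, and 8.5 refers to neither of them on this point.

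The first dose is handled differently. Section 8.3 says "Subjects will not be randomized until the echocardiogram and all lab results are finalized and reviewed by the Study Doctor", and Section 8.2 excludes boys with hyperkalemia at screening.

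**The concern.** Spironolactone is potassium-sparing and the subjects are boys aged 4 to 7. A site that follows 8.5 to the letter restarts the drug 7 days after a raised potassium, whether or not the value has been rechecked or has come down. The same holds for any other listed event that has not settled. The restart is thus less protected than the first dose.

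The drug supply does not act as a brake, because families hold a 90-day supply (7.4) and a restart usually needs no pharmacy step. For Grade 3 or 4 events, two sections give opposite instructions and no text says which prevails. With four to seven centers, the same event could be handled differently. What is at stake is participant safety and consistent conduct.

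**Working it through.** **1. Is there a condition on the restart anywhere else?** The other controls compare as follows.

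| Control | What it does | Is it a condition of restart? |
|---|---|---|
| 8.4, repeat labs | "Laboratory tests with values within the clinically significant range will be repeated during the same visit whenever possible"; a persisting abnormality may end participation after Monitor discussion | No. It sits under the baseline heading and, even if applied on study, confirms a value when found, not at the end of the hold |
| 10.1, repeat labs on study | Abnormal tests "may be repeated during visits whenever possible" | No. Permitted, not required |
| 8.5, intolerance | Withdrawal if the drug cannot be tolerated | No. No grade, no laboratory threshold |
| 11.3.2, notice to the Monitor | All serious events are notified | No. No reply is needed before restart |
| 11.4, enrollment halt | Applies to a "Grade 3 or higher adverse event toxicity that is unanticipated and possibly, probably, or definitely related to the study drug" | No. Anticipated events are outside it |
| 11.3.5 and 12.1 | Follow-up to resolution or stabilization; monthly laboratory review | No. Not linked to the restart |
| 18.2 | Changes allowed to protect subjects | No. It permits a departure from 8.5 |

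**2. Does the routine schedule supply a potassium result in time?** Inputs: scheduled electrolytes after the start of drug at Days 7, 30, 60, 90, 120, 150 and 180 (Table 3; Month 5 is taken as Day 150 because the table header is damaged), and a 7-day hold (8.5). Assume the hold starts on the day of the draw.

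Restart = draw day + 7. Gap = next scheduled draw − restart.

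| Draw | Restart | Next draw | Gap (days) |
|---|---|---|---|
| 7 | 14 | 30 | 16 |
| 30 | 37 | 60 | 23 |
| 60 | 67 | 90 | 23 |
| 90 | 97 | 120 | 23 |
| 120 | 127 | 150 | 23 |
| 150 | 157 | 180 | 23 |

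Scheduled draws inside the hold: 0 of 6. The ±3 day visit window (9.1) does not change this. The two closest draws would be Day 7 + 3 = 10 and Day 30 − 3 = 27, which are 17 days apart against a 7-day hold. With windows on both draws, the gap of 16 becomes 10 to 22 days (27 − 17 and 33 − 11), and the gap of 23 becomes 17 to 29 days (for Day 30: 57 − 40 and 63 − 34).

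Five of the six draws (Week 1 and Months 1, 2, 4 and 5) may be done off-site without a study-team visit (14.1). At those draws a same-visit repeat may not be possible.

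**3. Could the Clinical Safety Monitor step in before restart?** Under 11.3.2, a serious event that is not both unexpected and related reaches the Sponsor-Investigator within 7 days and the Monitor within a further 48 hours: 7 + 2 = 9 days, which is 9 − 7 = 2 days after the restart. If the event is classed as unexpected because of greater severity (11.1.2), the allowance is 48 + 48 hours = 4 days, before the restart. Both are maximum allowances.

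**4. Which instruction applies at Grade 3 or 4?** Under 11.1.3 these events are serious. Spironolactone is an oral drug taken daily for 6 months, and the protocol describes no infusion or observed dosing. The ordinary meaning of administration in 11.3.2 is therefore the treatment period, and the agent is to be stopped. Section 8.5 has no exception for these grades and says to re-challenge. The two conflict, and the text leans toward discontinuation.

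**The case against.** The strongest reply is that 8.5 does not stand alone. Testing potassium during the hold does not breach 8.5, since 10.1 allows a repeat, including at a laboratory near home. Section 8.4 may reach past baseline, because it speaks of terminating a subject from the study. Hyperkalemia and renal failure are excluded at entry (8.2), and ACE inhibitors and potassium supplements are prohibited (10.8.1). An unusually severe potassium event might count as unanticipated if 8.5 and 11.4 share the severity test in 11.1.2; it would then leave the re-challenge sentence, go to Monitor discussion and possibly halt enrollment. The Manual of Operating Procedures (18.1), which is not among the documents reviewed, may hold restart detail.

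These points lower the risk, but none conditions the restart. Testing is compatible with 8.5; delaying the restart because of the result is a departure from it. Section 18.2 permits departures that protect subjects, but 15.1 confines deviations to emergencies, and waiting for Grade 2 vomiting to settle may not be one. The terms unexpected and unanticipated are not equated in the protocol.

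One part of the reply stands in full. A reader might infer that at Grade 3 or 4 a site cannot tell whether to stop or re-challenge, or that the plan simply mandates re-challenge after a life-threatening event. That needs 11.3.2 to mean only an acute reaction around a dose, and nothing in the text supports so narrow a reading for a daily oral drug.

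**Conclusion.** The point holds and should be fixed. Section 8.5 states a rule, at a fixed 1 week, that makes no requirement of improvement or a potassium recheck; this is not merely missing detail. For related Grade 3 or 4 events it conflicts with 11.1.3 and 11.3.2, and a cross-reference settles the matter in favor of discontinuation.

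The size is 0 of 6 scheduled draws within the hold and a nominal 16 or 23 days from restart to the next routine potassium. These figures assume Month 5 at Day 150, a hold that starts on the draw day and no unscheduled test. A result that comes back later moves the hold and shortens the gap, and a hold started between draws for another event could contain a scheduled draw. The figures bear on potassium, not on most of the other listed events.

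Two further inferences are not supported. The gaps do not measure risk, because the documents give no event rate. Nothing here shows an effect on the primary equivalence test, and none is claimed.

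**What to change.** Amend Section 8.5 to:

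- (a) limit hold and re-challenge to Grade 2, and cross-refer related Grade 3 or higher events to 11.3.2;
- (b) make 1 week a minimum, and require documented resolution or improvement to a level set by the sponsor's clinicians;
- (c) for raised potassium, require a repeat result reviewed by the Study Doctor before restart, using the off-site laboratory route already allowed (10.1, 14.1);
- (d) state that doses held for safety do not count toward the 10% missed-dose criterion, and that boys taken off drug still attend the Month 6 assessment.

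Item (d) is needed because a longer hold could otherwise trigger withdrawal. Over about 180 daily doses, 10% is 18. A 1-week hold uses 7 and leaves 18 − 7 = 11. If held doses count, a hold of 19 days would exceed the limit and prompt the continuation discussion in the same section. The Month 6 provision matters because the power statement rests on 10 per group with 12 randomized, which leaves 12 − 10 = 2 per arm to lose.

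The cost is a few sentences and about one extra blood draw per potassium event. The downside is that some boys stay off drug for longer than 1 week, and boys with related Grade 3 or 4 events stop spironolactone.

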9. STUDY AGENT

Site pharmacies will dispense spironolactone and prednisolone per the site's standard procedures. In the rare instance of a subject not being able to tolerate prednisolone, an equivalent dose of prednisone may be provided as crushed tablets after approval by the Sponsor-Investigator.

9.1 Dispensing of Study Agent

Subjects will be provided a supply of study drug at Day 0 and Month 3 (Day 90). A +/- 3 day window is acceptable for all visits after Day 0.

9.2 Description of Study Drug

Table 2 Investigational Product

Product Name	Spironolactone, USP
Dosage Form	25mg/5mL Oral Suspension
Route of Administration	Oral
Physical Description	Spironolactone, USP is practically insoluble in water, soluble in alcohol and freely soluble in benzene and in chloroform. Carospir Oral suspension contains 25 mg of the aldosterone antagonist spironolactone per 5 mL. Inactive ingredients include sorbic acid, potassium sorbate, citric acid anhydrous, sodium citrate dehydrate, simethicone emulsion, saccharin sodium, xantham gum, Magnasweet 110, glycerin, banana flavor, and purified water.
Manufacturer	CMP Pharma, Inc.

Product Name	Prednisolone Sodium Phosphate*, USP
Dosage Form	15 mg/5 mL Solution
Route of Administration	Oral

Physical Description	Prednisolone Sodium Phosphate Oral Solution equivalent to 15 mg prednisolone per 5 mL contains the following inactive ingredients: alcohol 1.8%, dibasic sodium phosphate, glycerin, liquid sugar, monobasic sodium phosphate, natural and artificial grape flavor, purified water, sodium benzoate and sorbitol solution. It may contain 10% dibasic sodium phosphate solution and/or 10% monobasic sodium phosphate solution to adjust pH between 6.0 and 8.0. Prednisolone sodium phosphate occurs as white or slightly yellow, friable granules or powder. It is freely soluble in water; soluble in methanol; slightly soluble in alcohol and in chloroform; and very slightly soluble in acetone and in dioxane.
Manufacturer	Morton Grove Pharmaceuticals**

**Contact the NCH study team if substituting with prednisone tablets.*

*** If at any point the drug becomes unavailable from this manufacturer, another manufacturer can be used to obtain the drug until available from Morton Grove Pharmaceuticals.*

9.3 Potential Risks

Potential risks to study subjects include risks associated with administration of the study agent and with study procedures.

9.3.1 Risks Associated with Spironolactone

Common side effects associated with the use of spironolactone in this subject population may include: diarrhea, cramping, nausea, vomiting, somnolence, headache, ataxia, gynecomastia and urticaria.

9.3.2 Risks Associated with Corticosteroid Use

Common side effects associated with the use of prednisolone in this subject population may include: depression, euphoria, emotional instability, headache, seizures, vertigo, body fluid retention, hypernatremia, hypertension, acne, bruising, wound healing impairment, decreased body growth, increased risk of infection, diaphoresis, abdominal distention, pancreatitis, peptic ulcers, ulcerative esophagitis, hepatic impairment, steroid myopathy, and muscle weakness. Serious side effects may include: anaphylaxis, Cushing's syndrome, hyperglycemia, and primary adrenocortical insufficiency.

10. STUDY PROCEDURES AND SCHEDULE

Subjects will complete study assessments monthly via online survey, phone, or at clinic visits for 6 months.

10.1 Laboratory Procedures/Evaluations

Laboratory tests with values within the clinical significant range may be repeated during visits whenever possible. If the test result returns after the subject leaves the clinic and the Study Doctor wants additional tests, they will be immediately contacted. Subjects may be asked to return to the outpatient clinic for a repeat test. For non-local subjects, arrangements can be made to have the blood test redrawn in a laboratory close to home or by their primary care physician.

10.1.1 Clinical Laboratory Evaluations

Functional Testing

- 100 meter timed test (100M)
- Strength testing and Dynamometry
- North Star Ambulatory Assessment (NSAA)
- 4-stair climb
- Time to arise from floor

Blood Chemistry

Chemistry analysis will include the following at specified visits:

- Creatine Kinase (Visits 1, 8)
- Gamma Glutamyl Transferase (GGT) (Visits 1, 5, 8)
- Creatinine (Visits 1, 5, 8)
- Blood Urea Nitrogen (BUN) (Visits 1, 5, 8)
- Glucose (Visits 1, 5, 8)
- Cystatin C (Visits 1, 5, 8)
- Electrolytes (Sodium, Potassium, Chloride, CO₂) [All Visits]

Cardiac

Echocardiogram (Echo) will be conducted at the time points specified in Table 3.

Research Blood Sample

Blood samples will be collected for future research purposes, to examine/research potential disease modifiers and/or biomarkers. Research blood samples may be distributed for future research to [name], at Ohio State University, a Co-Investigator on this study.

10.2 Study Visits

10.2.1 Timeline

Table 3 Schedule of Assessments

Assessment	Visit 1	Study Drug Start ¹	Visit 2	Visit 3	Visit 4	Visit 5	Visit 6	Visit 7	Visit 8
	Screening		Week 1	Month 1	Month 2	Month 3	Month 4	Month 5	Month 6
	Day -14 to 0		Day 0	Day 7	Day 30	Day 60	Day 90	Day 120	Day 180
Research Purposes Only									
Echocardiogram (Echo) ²	X								X
Biomarkers Blood Draw (plasma and white blood cells)	X								X
Strength Testing/Dynamometry	X					X			X
Standard of Care									
Informed Consent	X								
AE Assessment		X	X	X	X	X	X	X	X
Concomitant Medications	X	X	X	X	X	X	X	X	X
Physical Exam	X					X			X
Skin Exam	X					X			X
Cushingoid Exam	X					X			X
Medical History Review	X					X			X
100 Meter Timed Test	X					X			X
Parent Survey			X	X	X		X	X	
4-Stair Climb	X					X			X
North Star Ambulatory Assessment (NSAA)	X					X			X
Time to Arise from Floor	X					X			X
Creatine Kinase	X								X
Gamma Glutamyl Transferase (GGT)	X					X			X
Creatinine	X					X			X
Blood Urea Nitrogen (BUN)	X					X			X
Glucose	X					X			X
Cystatin C	X					X			X
Electrolytes ³	X		X	X	X	X	X	X	X
Medication Dispensing ⁴		X ¹				X			
Vitals	X					X			X

1. Study drug will be dispensed and treatment initiated once eligibility is confirmed following receipt and review of results from screening visit procedures. The day study drug is started is considered Day 0.

2. A clinical echocardiogram within the previous 30 days prior to screening is acceptable for screening purposes.
3. Includes: Sodium, Potassium, Chloride, CO₂
4. Medication dispensing will occur every 90 days, beginning at the time of randomization.

